4.3 Screen Failures and Rescreening

Screen failures are defined as subjects who consent to participate in the clinical study but are not subsequently enrolled (i.e., randomized) into the study. A minimal set of screen failure information will be collected that includes demography, screen failure details, eligibility criteria, medical history, prior therapies, and any serious TEAEs.

Individuals who do not meet the criteria for participation in this study (screen failure) may be rescreened. Refer to Section [7.1.1](#).

4.4 Subject Number and Identification

Subjects will have a unique identification number used at screening. Subjects will be assigned a unique subject number at randomization. Assignment of subject numbers will be in ascending order and no numbers will be omitted (e.g., Subjects 0101, 0102, 0103). Replaced subjects will

be assigned a subject number corresponding to the number of the subject he/she is replacing plus 1000 (e.g., Subject 1101 replaces Subject 0101).

Subjects will be identified by subject number only on all study documentation. A 1-digit site identification number will be added to the subject number when entering the subject into the database (example: site 1, Subject 0101 will be entered as 10101 into the database). A list identifying the subjects by subject number will be kept in the Site Master File.

4.5 Subject Withdrawal and Replacement

A subject is free to withdraw from the study at any time. In addition, a subject will be withdrawn if any of the following criteria are met:

- change in compliance with any inclusion/exclusion criterion that is clinically relevant and affects subject safety as determined by the Investigator (or designee)
- noncompliance with the study restrictions that might affect subject safety or study assessments/objectives, as considered applicable by the Investigator (or designee)
- any clinically relevant sign or symptom that, in the opinion of the Investigator (or designee), warrants subject withdrawal.

If a subject is withdrawn after randomization and prior to receiving Olpasiran dose, the Sponsor will be notified and the date and reason(s) for the withdrawal will be documented in the subject's electronic Case Report Form (eCRF). If a subject is withdrawn, efforts will be made to perform all EOS assessments, if possible ([Appendix 9](#)). Other procedures may be performed at the Investigator's (or designee's) and/or Sponsor's discretion. If the subject is in-house, these procedures should be performed before the subject is discharged from the CRU. The Investigator (or designee) may also request that the subject return for additional follow-up visits. All withdrawn subjects will be followed until resolution of all their TEAEs or until the unresolved TEAEs are judged by the Investigator (or designee) to have stabilized.

Subjects who are withdrawn for reasons not related to study drug may be replaced following discussion between the Investigator and the Sponsor. Subjects withdrawn as a result of TEAEs thought to be related to the study drug will generally not be replaced.

4.6 Study Termination

The Sponsor may stop the study or study site participation in the study for medical, safety, regulatory, administrative, or other reasons consistent with applicable laws, regulations, and GCP. Both the Sponsor and the Investigator reserve the right to terminate the Investigator's participation in the study according to the Clinical Trial Agreement. The Investigator is to notify

the Ethics Committee (EC) in writing of the study's completion or early termination and send a copy of the notification to the Sponsor.

In addition, the study may be terminated by the Sponsor at any time and for any reason. If the Sponsor decides to terminate the study, the Sponsor will inform the Investigator as soon as possible.

5. STUDY TREATMENTS

Study treatment is defined as the investigational product intended to be administered to a study subject according to the study protocol.

The Investigational Product Instruction Manual (IPIM), a document external to this protocol, contains detailed information regarding the storage, preparation, destruction, and administration of the investigational medicinal product (IMP) shown in [Table 2](#) and [Appendix 8](#)

5.1 Investigational Product

The IMP will be supplied by the Sponsor.

All supplies of investigational product, both bulk and subject-specific, will be stored in accordance with the manufacturer's instructions or pharmacy instructions. Until dispensed to the subjects, the investigational products will be stored at the study site in a location that is locked with restricted access.

Table 2. Investigational Product

Abbreviations: CRF = case report form; SC = subcutaneous.

^a Olpasiran will be manufactured and packaged by Amgen and distributed using Amgen clinical study drug distribution procedures.

^b Provided as a [REDACTED], with maximum deliverable volume of up to [REDACTED] mL from each vial of [REDACTED] mg/mL Olpasiran. Each [REDACTED] mL).

5.2 Treatment of Overdose

Treatment overdose is not applicable to this study.

5.3 Randomization

Subjects will be randomized in a 1:1 ratio to 1 of 2 groups (A or B) as shown in [Table 1](#), in an open-label manner.

Labcorp will provide a computer-generated randomization schedule to the site to be used for treatment assignments. Subjects will be assigned a subject number based in sequential order in which they qualified to be randomized, in accordance with the randomization schedule. Subjects are considered randomized once a unique subject number has been assigned. Dosing should occur within 1 day (\leq 24 hours) of randomization. If dosing cannot occur within 1 day of randomization, the Medical Monitor may be contacted to approve dosing outside the 24-hour

window (up to an additional 24 hours after randomization). The randomization date is to be documented in the subject's medical record and on the enrollment CRF.

5.4 Blinding

This is an open label study; blinding procedures are not applicable.

5.5 Treatment Compliance

Treatment compliance is not applicable to this study.

5.6 Drug Accountability

Guidance and information on preparation, handling, storage, accountability, destruction, or return of the investigational product during the study are provided in the IPIM.

6. CONCOMITANT THERAPIES AND OTHER RESTRICTIONS

6.1 Concomitant Therapies

Throughout the study, investigators may prescribe any concomitant medications or treatments deemed necessary to provide adequate supportive care except for the following:

- Use of any over-the-counter or prescription medications within 14 days or 5 half-lives (whichever is longer), before dosing on Day 1 and during the study, unless to treat a TEAE
 - Use of any herbal medicines, vitamins, or dietary supplements known to affect lipid metabolism (e.g., fish oils > 1000 mg/day, red yeast rice extract), within 30 days before dosing on Day 1 and for the duration of the study.

The following concomitant therapies are allowed:

- Acetaminophen (paracetamol) up to 2 g/day for analgesia
- Hormone replacement therapy (e.g., estrogen, thyroid) provided the subject is stable on replacement therapy
- Medication for the management of arterial hypertension, including, but not limited to, angiotensin-converting enzyme inhibitors, angiotensin receptor blockers, beta blockers, calcium channel blockers, or low dose thiazides, provided it is stable (i.e., no change in drug or dose) for at least 8 weeks prior to enrollment
- Use of anti-platelet therapy (low-dose acetylsalicylic acid [up to 162.5 mg daily], clopidogrel, or ticagrelor) is allowed, provided subjects have been on a stable dose for at least 6 weeks prior to enrollment and plan to be on the same dose for the duration of the study
- If subjects are on statin, subjects must be on a stable dose of the same statin for at least 6 weeks prior to enrollment, and plan to remain on the same dose (i.e., no change in medication or dosage) for the duration of the study
- Use of ezetimibe is allowed, provided subjects have been on a stable dose for at least 6 weeks prior to enrollment and plan to be on the same dose for the duration of the study

- Medication used to manage chronic conditions not excluded by other exclusion criteria, provided subjects have been on a stable dose for at least 6 weeks prior to enrollment and plan to be on the same dose for the duration of the study. Medication must be reviewed and approved by the Investigator (or designee) and acknowledged by the Sponsor. Written documentation of this review and Sponsor acknowledgement is required for subject participation.
- All herbal medicines (e.g., St. John's wort) and dietary supplements (with the exception of those known to affect lipid metabolism, which are excluded above) consumed by the subject within the 30 days prior to Check-in and continue use during the study, which are deemed acceptable by the Investigator (or designee) and in consultation with the Sponsor.

Concomitant therapies are to be collected from informed consent through the EOS. Any medication taken by a subject during the course of the study and the reason for its use will be documented in the source data.

6.2 Diet

While confined at the study site, subjects will receive a standardized diet at scheduled times that do not conflict with other study-related activities. Subjects will be fasted overnight (at least 10 hours) before collection of blood samples for clinical chemistry evaluations or lipids.

Alcohol consumption will not be allowed from 48 hours prior to Check-in until end of in-house residency period.

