4.2 Exclusion Criteria

Subjects will be excluded from the study if they satisfy any of the following criteria prior to enrollment unless otherwise stated:

1. History or clinical evidence of peripheral neuropathy.
2. Currently receiving apheresis as lipid reducing therapy.
3. History or clinical evidence of bleeding diathesis or any coagulation disorder, including prothrombin time (PT), activated partial thromboplastin time (APTT), or platelet count outside of the laboratory's normal reference range at screening. Subjects with PT and/or APTT values that are outside of the laboratory's normal reference range at screening may still be eligible to proceed to enrollment if the results are judged by the investigator in consultation with the study medical monitor to not be clinically significant.
4. History or clinical evidence of diabetes mellitus, including a fasting glucose ≥ 125 mg/dL (6.9 mmol/L) at Screening.
5. History or evidence, at Screening or Check-in, of clinically significant disorder, condition, or disease not otherwise excluded that, in the opinion of the Investigator (or designee), would pose a risk to subject safety or interfere with the study evaluation, procedures, or completion.

Exceptions include:

- a. Subjects with controlled and stable arterial hypertension. Controlled and stable hypertension with a systolic blood pressure [BP] < 150 mmHg or diastolic BP < 90 mmHg at Screening and Day -1, with no change in medication and dosage for at least 8 weeks prior to enrollment and expected to remain on this dose and medication for the entire duration of the study. If the initial BP is elevated, the reading may be repeated again at least 15 minutes later and the lower of the 2 readings may be used.
- b. Subjects with diagnosis of hyperlipidemia on treatment with a stable dose of the same statin (with or without concomitant ezetimibe) for at least 6 weeks prior to enrollment and expected to remain on this dose and medication for the entire duration of the study.
6. A QT interval corrected for HR based on the Fridericia correction (QTcF) interval > 450 msec in male subjects or > 470 msec in female subjects or history/evidence of long QT syndrome, at Screening.
7. Subject has known sensitivity to any of the products or components to be administered during dosing.
8. Estimated glomerular filtration rate (eGFR) less than 60 mL/min/1.73 m² as calculated by the Modification of Diet in Renal Disease (MDRD) equation, at Screening.

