 - g. Medication used to manage chronic conditions not excluded by other exclusion criteria, provided subjects have been on a stable dose for at least 6 weeks prior to enrollment and plan to be on the same dose for the duration of the study. Medication must be reviewed and approved by the Investigator (or designee) and acknowledged by the Sponsor. Written documentation of this review and Sponsor acknowledgement is required for subject participation.
12. Subjects are on niacin, or have received niacin > 200 mg/day within 3 months prior to dosing on Day 1.
13. Use of any herbal medicines, vitamins or dietary supplements known to affect lipid metabolism (e.g., fish oils > 1000 mg/day, red yeast rice extract), within 30 days prior to dosing on Day 1 and for the duration of the study.
14. All herbal medicines (e.g., St. John's wort) and dietary supplements (with the exception of those known to affect lipid metabolism, which are excluded above) consumed by the subject within the 30 days prior to Check-in, unless deemed acceptable by the Investigator (or designee) and in consultation with the Sponsor.
15. Triglycerides \geq 5.65 mmol/L (i.e., 500 mg/dL) at Screening
16. History of drug/chemical abuse within 1 year prior to Check-in.
17. Alcohol consumption within 48 hours prior to Check-in and during in-house residency period.

18. Alcohol consumption of > 14 units per week for males and > 7 units per week for females. One unit of alcohol equals 12 oz (360 mL) beer, 1½ oz (45 mL) liquor, or 5 oz (150 mL) wine.
19. Positive test for illicit drugs and/or alcohol use at Screening or Check-in.
20. Female subjects with a positive pregnancy test at Screening or Check-in.
21. Female subjects lactating/breastfeeding or who plans to breastfeed during the study through 90 days after Olpasiran dosing.
22. Unwilling to abstain from sperm donation through 90 days after Olpasiran dosing (see [Appendix 4](#)).
23. Male subjects with a female partner of childbearing potential and not willing to inform his partner of his participation in this clinical study.
24. Male subjects with a pregnant partner or partner planning to become pregnant while the subject is on study through 90 days after Olpasiran dosing.
25. Subject has received a dose of an investigational drug within the past 30 days or 5 half-lives, whichever is longer, prior to Check-in. Other investigational procedures while participating in this study are excluded.

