6.3 Exercise

Subjects will abstain from strenuous exercise for 72 hours before each blood collection for clinical laboratory tests. Subjects may participate in light recreational activities during the study (e.g., watching television, walking, reading).

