Appendix 2. Clinical Laboratory Evaluations

Table 3. Safety Laboratory Evaluations

Clinical chemistry:	Hematology:	Urinalysis:
Alanine aminotransferase	Hematocrit	Bilirubin
Albumin	Hemoglobin	Blood
Alkaline phosphatase	Mean cell hemoglobin	Color and appearance
Aspartate aminotransferase	Mean cell hemoglobin-concentration	Glucose
Blood urea nitrogen or urea	Mean cell volume	Ketones
Calcium	Platelet count	Leukocyte esterase
Chloride	Red blood cell (RBC) count	Nitrite
Cholesterol	RBC distribution width	pH
Creatinine	White blood cell (WBC) count	Protein
Direct bilirubin ^a	WBC differential:	Specific gravity
Gamma-glutamyl transferase	Basophils	Urobilinogen
Glucose (fasting)	Eosinophils	Microscopic examination (if protein, leukocyte esterase, nitrite, or blood is positive)
Indirect bilirubin ^a	Lymphocytes	
Inorganic phosphate	Monocytes	
Lactate ^h	Neutrophils	
Magnesium		Hormone panel - females only:
Phosphorous		Follicle-stimulating hormone ^b (postmenopausal females only)
Potassium		Serum pregnancy test (human chorionic gonadotropin) ^d
Sodium		Urine pregnancy test ^d
Total bilirubin ^a		
Total cholesterol		
Total CO ₂ (measured as: bicarbonate)		
Total creatine kinase		
Total protein		
Tryptase ^g		
Uric acid		

Footnotes defined on last page of the table

Page 1 of 2

Table 3. Safety Laboratory Evaluations

Serology^b:	Drug screen^c:	Other Tests:
Anti-hepatitis B surface antibody	Including, but not limited to: Amphetamines/methamphetamines	Estimated glomerular filtration rate (eGFR) ^{b, f}
Anti-hepatitis B core antibody	Barbiturates	
Hepatitis B surface antigen	Benzodiazepines	
Hepatitis C antibody	Cocaine	
Human immunodeficiency virus antibodies	Methadone	
	Phencyclidine	
Coagulation Panel:	Opiates	
International normalized ratio (INR) ^e	K2 (Synthetic cannabinoids)	
Prothrombin time (PT)	Tricyclic antidepressants	
Activated partial thromboplastin time (APTT)	Cotinine test	
	Alcohol urine test	

^a Direct and indirect bilirubin will be analyzed if total bilirubin is elevated.

^b Only analyzed at Screening.

^c Only analyzed at Screening and Check-in.

^d Performed in serum at Screening and in urine at all other times for all females. A positive urine pregnancy test will be confirmed with a serum pregnancy test.

^e International normalized ratio will be tested if hepatotoxicity is suspected guidelines presented in [Appendix 7](#)

^f Estimated glomerular filtration rate will be calculated by the Modification of Diet in Renal Disease (MDRD) equation.

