8.6.2. Clinical Laboratory Parameters

All clinical laboratory parameters will be listed; any value outside the clinical reference range will be flagged. Separate listings will be provided for any parameter for which there is any individual subject value outside the respective clinical reference range.

Summary tables by timepoint along with change from baseline and percent change from baseline will be provided for clinical chemistry and hematology parameters based on safety analysis set. The baseline is defined as the last reading before dosing.

Values recorded as $<x$, $\leq x$, $>x$, or $\geq x$ will be displayed in the listings as recorded. For the derivation of listing flags and calculation of summary statistics, $<x$ and $\leq x$ values will be set to BLQ, whereas $>x$ and $\geq x$ values will be set to x.

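### Liver chemistry and six of the seven lipids have a baseline taken under required alcohol abstinence, but outpatient follow-up samples have no alcohol rule and no record of intake.

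*Protocol*

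**What the plan says.** Protocol 6.2 limits alcohol as follows: "Alcohol consumption will not be allowed from 48 hours prior to Check-in until end of in-house residency period". Exclusion criterion 17 in Protocol 4.2 sets the same window ("Alcohol consumption within 48 hours prior to Check-in and during in-house residency period"). Appendix 9 places residency from Day -1 to Day 4.

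Habitual intake is capped by exclusion criterion 18 ("Alcohol consumption of > 14 units per week for males and > 7 units per week for females"). It is an entry criterion, since the list opens with "Subjects will be excluded from the study if they satisfy any of the following criteria prior to enrollment unless otherwise stated". A positive test also excludes ("Positive test for illicit drugs and/or alcohol use at Screening or Check-in"), and the footnote to Appendix 2, Table 3 says of the drug and alcohol screen: "Only analyzed at Screening and Check-in". Alcohol use is asked about in the medical history at Screening, with an interim history at Check-in (Protocol 7.2.5).

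Two other conditions follow every relevant draw. Protocol 6.2 requires an overnight fast of at least 10 h before chemistry and lipid samples. Protocol 6.3 says: "Subjects will abstain from strenuous exercise for 72 hours before each blood collection for clinical laboratory tests".

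For laboratory safety data, SAP 8.6.2 says: "The baseline is defined as the last reading before dosing". For PD parameters, SAP 8.5.4 instead averages the two most recent available predose values, or uses the single value if only one exists. Screening lipids consist of triglycerides only (Protocol 7.4.1, SAP 8.5.4). Both randomized groups receive olpasiran, and results are summarised as change and percent change from baseline by group.

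**The concern.** Fasting and exercise are matched between baseline and follow-up; alcohol is not. It is barred before the baseline samples and left open before the outpatient ones, so the difference in conditions runs the same way at every outpatient visit. Random within-subject variation averages out over subjects and visits, but a systematic difference of this kind does not.

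Lipids are a secondary endpoint, and liver enzyme elevation is a named important potential risk (Protocol 1.5.2). If drinking after discharge moved GGT, AST, VLDL-C or another of these analytes, the movement would appear in the tables as change from baseline on olpasiran. There is no untreated group showing the same drift and no intake record to help interpret it.

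**Working it through.** **1. Sample counts.** Column alignment in Tables 5 and 6 of Appendix 9 is damaged in the available text, so the counts were checked against the maxima in Appendix 3.

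- Lipid panel: Screening + Day 1 predose + 5 in Table 6 = 7, which matches Appendix 3 (7). All 5 post-dose panels are outpatient.
- Chemistry: Screening + Check-in + 2 in-house post-dose + 8 in Table 6 = 12, which matches Appendix 3 (12). Of 2 + 8 = 10 post-dose samples, 8 are outpatient.

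**2. Which baselines lie inside the abstinence window.**

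| Measure | Baseline under the SAP | Under the 48 h rule? |
|---|---|---|
| Liver chemistry | Last predose reading, which by the schedule is Check-in | Yes |
| VLDL-C, LDL-C, HDL-C, total cholesterol, Apo A1, Apo B | Day 1 predose, the only predose value | Yes |
| Triglycerides | Mean of Screening and Day 1 predose | Day 1 only |

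Screening has a urine alcohol test but no 48 h rule.

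**3. Effect of the baseline rule.** Suppose unrestricted drinking raises a value by a fraction d over the abstinent state, there is no drug effect, and the Screening sample is unrestricted. The apparent change is then:

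- single in-window baseline: (1 + d)/1 − 1 = d
- mean of Screening and Day 1: (1 + d)/(1 + d/2) − 1

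| d (assumed) | Single baseline | Mean baseline (triglycerides) |
|---|---|---|
| 5% | 5.0% | 2.4% |
| 10% | 10.0% | 4.8% |
| 20% | 20.0% | 9.1% |

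**4. Group-level size for triglycerides.** All inputs here are assumptions; the documents supply none of them. A fraction f = 25% to 50% of subjects drink in the 48 h before an unrestricted sample, and their triglycerides are e = 10% to 25% higher.

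- Mean rise in unrestricted samples, fe: 0.25 × 0.10 = 2.5% to 0.50 × 0.25 = 12.5%
- Apparent change with the SAP baseline, (1 + fe)/(1 + fe/2) − 1: 1.025/1.0125 − 1 = 1.2% to 1.125/1.0625 − 1 = 5.9%

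For comparison, take n = 12 per group and an assumed within-subject CV of 20% to 30%. With a two-value baseline the standard error of the mean percent change is about CV × √1.5/√12:

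- CV 20%: 0.20 × 1.225/3.464 = 7.1%
- CV 30%: 0.30 × 1.225/3.464 = 10.6%

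The shift is therefore between 1.2/10.6 ≈ 0.1 and 5.9/7.1 ≈ 0.8 standard errors.

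For analytes with a single in-window baseline, whatever shift applies carries through in full rather than by about half. The inputs above were chosen for triglycerides, so no size is claimed for liver enzymes or the other lipids.

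**The case against.** The strongest case on the other side is that this matters little.

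- **Purpose.** The primary endpoints are Cmax and AUC. Protocol 3.2 and 3.3 aim at comparing PK and Lp(a) reduction with the first-in-human study, and Protocol 1.1 describes Lp(a) as largely insensitive to environment. Other lipids are summarised descriptively, with no inference. All of this stands.
- **Existing safeguards.** Subjects are in good health, intake is capped at entry, and a fast precedes each chemistry or lipid draw. Appendix 7 prompts an alcohol history and lists alcoholic hepatitis as an alternative cause when ALT or AST rises above its thresholds. A reader might infer that a marked elevation would pass unquestioned as a drug effect; Appendix 7 does not support that. What remains is smaller drift below those thresholds, for which no alcohol information is collected.
- **Scope.** A reader might infer that every alcohol effect would be reported as an olpasiran effect. That goes too far. The randomized comparison of Group A with Group B is not systematically biased, because both groups follow the same rules. The two in-house post-dose chemistry samples are taken under the same rule as baseline. Nor are all lipid baselines fully abstinent, since half of the triglyceride baseline comes from Screening.
- **Preference.** No passage contradicts another. The standardized diet also applies only in-house, so an alcohol rule alone would not equalise conditions. The documents do not say how the first-in-human study handled alcohol before outpatient visits, so the effect on cross-study comparability cannot be judged. These points limit the benefit of a change but show no real harm from it.

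**Conclusion.** The point holds in a limited form. For liver chemistry and the six non-triglyceride lipids, an abstinent baseline is compared with outpatient samples that carry no alcohol rule and no intake record. This covers all 5 post-dose lipid panels and 8 of 10 post-dose chemistry samples. Within-group change at those visits can include an alcohol component that the design cannot separate from drug.

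The size is unknown. The only figure offered, about 0.1 to 0.8 standard errors for triglycerides, rests on the assumed drinking fraction, alcohol effect and within-subject CV, and on treating the Screening sample as unrestricted. The documents do not support a claim of material bias in any endpoint, and the conclusions on PK and Lp(a) are untouched. This is an optional improvement, not a flaw that threatens the study.

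**What to change.** In Protocol 6.2, extend the existing 48 h alcohol condition to each outpatient visit with a chemistry or lipid draw, in the way 6.3 already does for exercise. Add one eCRF question at those visits on whether it was kept, so that non-adherent samples can be flagged in the listings.

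The cost is one sentence in the protocol and subject instructions, one eCRF item, and a small added burden for subjects. No visit, sample size or planned analysis changes.

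If the visits are already complete, state the limitation in the clinical study report where outpatient lipid and liver-enzyme changes from baseline are interpreted.
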